14.5.3. Reporting Standards for Pharmacokinetic Data

Pharmacokinetic Concentration Data	
Descriptive Summary Statistics, Graphical Displays and Listings	Refer to IDSL PK Display Standards. Refer to IDSL Statistical Principle 6.06.1. Note: BLQ concentration values will be imputed as per GUI_51487 for descriptive summary statistics only.
NONMEM/Pop PK File	Pop-PK file (CSV and SAS format) for the POP-PK and POP-PKPD analyses performed by the Clinical Pharmacology Modelling and Simulation function will be created according to the POP-PKPD Dataset Specification document.
Pharmacokinetic Parameter Data	
Descriptive Summary Statistics, Graphical Displays and Listings	Refer to IDSL PK Display Standards. Refer to IDSL Statistical Principle 6.06.1.

14.6. Appendix 6: Derived and Transformed Data

14.6.1. General

Multiple Measurements at One Analysis Time Point

 Unless otherwise specified, if there are multiple measurements reported under the same nominal visit, the value of the first assessment will be used in any derivation of summary statistics, all individual measurements will be presented in any data listings. Participants with post-baseline safety data in both High and Low categories with respect to the Normal Range/Potential Clinical Concern will be counted in each of the categories for the “Any visit post-baseline” row of any related summary tables.
Study Day

 Calculated as the number of days from the first dose of study medication (IP start date). 
 If Visit Date = Missing → Study Day = Missing If Visit Date < First Dose Date → Study Day = Visit Date – IP Start Date If Visit Date ≥ First Dose Date → Study Day = Visit Date – (IP Start Date) + 1

14.6.2. Analysis Population

Actual Treatment for Safety Population

 Analysis of safety data will be by actual treatment arm. For participants identified as having any discrepancies between the treatment group they were randomised to and the treatment received, the actual treatment arm will be derived based on the treatment received for more than 50% of all treatment administrations. For all other participants, actual treatment arm will be the same as the randomised treatment arm.

14.6.3. Study Population

Demographics
Age

 Year of birth is collected as ‘YYYY’ and will be presented as collected in listings Date of birth will be imputed as ‘30th June YYY’ Age is calculated according to GSK standard IDSL algorithms and is based on the imputed date of birth relative to the date of Visit 1 (Screening).
BMI

 BMI will be calculated as Weight (kg) / [Height (m)]²

Exposure
Extent of Exposure (Therapeutic Coverage)

 IP is administered approximately every 4 weeks and each dose viewed as providing therapeutic coverage for 4 weeks (28 days). Duration of exposure is calculated based on the therapeutic coverage as follows: 
 Duration of Exposure (days) = (IP Stop Date – IP Start Date + 29) Duration of Exposure (months) = (IP Stop Date – IP Start Date + 29) * 12/365.25

Exposure
Extent of Exposure (Therapeutic Coverage)

 Subject Years Exposure is calculated as follows; 
 Subject Years Exposure = $(IP\ Stop\ Date - IP\ Start\ Date + 29)/365.25$ If the IP start date is missing and there is evidence the participant received at least one dose of IP, the IP start date will be taken to be the date of randomisation, if the IP end date is missing it will be taken to be the last on-treatment visit attended. Randomised participants with no evidence of receiving at least one dose of IP will be considered as having zero days of exposure.

Exposure for treatment period and no-treatment follow-up
Number of years on and off-treatment or missing

 All participants are expected to participate in the study for at least 52 weeks (± 7 days) The number of years on-treatment will be calculated as follows: 
 $(IP\ Stop\ Date - IP\ Start\ Date + 29)/365.25$ The number of years off-treatment will be calculated as follows: 
 $Date\ of\ Phase\ Conclusion - (IP\ stop\ date + 28)/365.25$ The number of years missing will be calculated as follows for subjects who withdrew from study: 
 $1 - (number\ of\ years\ on-treatment) - (number\ of\ years\ off-treatment)$
Duration of time in no-treatment follow-up

 This will be calculated in months for subjects who enter no-treatment follow-up after Week 52 as follows: 
 $(Date\ of\ study\ end - Date\ of\ Week\ 52) * 12/365.25$

Concomitant Medications (CM)
Time since first dose (days)

 The time since first dose will be calculated as follows: If CM start date < IP start date = CM start date - IP start date If CM start date \geq IP start date = CM start date – IP Start Date + 1 Missing otherwise. The duration in days will be calculated as follows: CM end date – CM start date + 1

NOTES: Please refer to [Appendix 7: Reporting Standards for Missing Data](#) for handling of missing and partial dates

Subgroups
Participants With Asthma

 Concurrent asthma: Subjects with a response of 'Current' for the medical condition of 'Asthma'. No concurrent asthma: Subjects with a response of 'Past', 'Not Assessed' or 'No Medical Condition' for the medical condition of 'Asthma'. Subjects with a missing response will also be included in this category.

Subgroups										
Aspirin Exacerbated Respiratory Disease (AERDS)										

 • Current AERDS: Subjects with a response of 'Current' for the medical condition of 'Drug Allergy'. • No Current AERDS: Subjects with a response of 'Past', 'Not Assessed' or 'No Medical Condition' for the medical condition of 'Drug Allergy'. Subjects with a missing response will also be included in this category. 										
Number of previous surgeries										

 • Participants will be categorised as follows based on data collected on the eCRF regarding number of previous surgeries: 1, 2, >2 										
Baseline Blood Eosinophil Categories										

 • Categories for baseline blood eosinophils will be: 
 ○ ≤ 0.3 GI/L; >0.3 to ≤ 0.5 GI/L; >0.5 to ≤ 0.7 GI/L; >0.7 GI/L • Blood eosinophils are reported in GI/L, each category is rounded to 1 d.p. which is equivalent to rounding blood eosinophils to the nearest 100 cells/μL. 										
Region										

 • Europe: Participants from sites in Germany, Netherlands, Romania, Sweden, UK • United States: Participants from sites in US • Rest of World: Participants from sites in South Korea, Argentina, Australia, Canada, Russia 										
Age Categories										

 • Participants will be categorised as follows based on the derived age: • 18-<40 years, 40 - < 65 years, ≥ 65 years. 										
Race Categories										

 • Subjects will be categorised by Race based on the Geographic Ancestry reported on the eCRF: 
  
 Race Category	Geographic Ancestry reported on the eCRF	
   
 African American/African Heritage	African American/African Heritage	
 
 White	White – Arabic/North African Heritage White – White/Caucasian/European Heritage	
 
 Asian	Asian – Central/South Asian Heritage Asian – East Asian Heritage Asian – Japanese Heritage Asian – South East Asian Heritage	
 
 Other	American Indian or Alaskan Native Native Hawaiian or Other Pacific Islander Multiple Race	
  
	Race Category	Geographic Ancestry reported on the eCRF	African American/African Heritage	African American/African Heritage	White	White – Arabic/North African Heritage White – White/Caucasian/European Heritage	Asian	Asian – Central/South Asian Heritage Asian – East Asian Heritage Asian – Japanese Heritage Asian – South East Asian Heritage	Other	American Indian or Alaskan Native Native Hawaiian or Other Pacific Islander Multiple Race
Race Category	Geographic Ancestry reported on the eCRF									
African American/African Heritage	African American/African Heritage									
White	White – Arabic/North African Heritage White – White/Caucasian/European Heritage									
Asian	Asian – Central/South Asian Heritage Asian – East Asian Heritage Asian – Japanese Heritage Asian – South East Asian Heritage									
Other	American Indian or Alaskan Native Native Hawaiian or Other Pacific Islander Multiple Race									

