6. STUDY POPULATION ANALYSES

6.1. Overview of Planned Study Population Analyses

All displays will be based on the ITT population, unless otherwise specified.

Study population displays including summaries of subject disposition, protocol deviations, demographic and baseline characteristics, prior and concomitant medications and treatment exposure will be based on GSK Core Data Standards. Additional summary information showing the amount of time within the 52-week treatment period considered as on-treatment, off-treatment and missing will be presented.

A summary of subject disposition and duration of time spent in the no-treatment follow-up will be provided for the subset of participants who participated in the 6-month no-treatment follow-up.

Details of the planned displays are presented in [Appendix 12: List of Data Displays](#).

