14.4.1.1. Phases for Efficacy Assessments

Study Phase	Definition
Pre-Treatment	Assessment Date \leq Interventional Product Start Date
On-Treatment	Participants who did not withdraw early from Interventional Product: Interventional Product Start Date < Assessment Date \leq Earlier of Interventional Product Stop Date +28 days / Week 52 Visit Date Participants who withdrew early from Interventional Product: Interventional Product Start Date < Assessment Date \leq Earlier of Interventional Product Stop Date +28 days/Date of Phase Conclusion
Off-Treatment	Participants who did not withdraw early from Interventional Product: Interventional Product Stop Date +28 days < Assessment Date \leq Week 52 Visit Date Participants who withdrew early from Interventional Product: Interventional Product Stop Date + 28 days < Assessment Date \leq Date of Phase Conclusion
Off-Treatment (Follow-up after Week 52)	Participants who enter the follow-up period after Week 52: Week 52 Visit Date < Assessment Date

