14.12.4. Study Population Tables

Study Population Tables					
No.	Population	IDSL / Example Shell	Title	Programming Notes	Deliverable [Priority]
Subject Disposition					
1.1.	ITT	SD1	Summary of Treatment Status and Reasons for Discontinuation of Study Treatment	ICH E3	SAC [1]
1.2.	ITT	SHELL	Summary of Time On- and Off-Treatment by Withdrawal Scenario	Withdrawal scenarios are detailed in Section 14.7.2.3. Add footnote to indicate exclusion of data from the follow-up period after Week 52	SAC [2]
1.3.	ITT	ES1	Summary of Subject Disposition (Week 52)	ICH E3, FDAAA, EudraCT	SAC [1]
1.4.	FU	ES1	Summary of Subject Disposition (Follow-Up Period after Week 52)		SAC [2]
1.5.	FU	SHELL	Summary of Duration of Time in Follow-Up Period after Week 52		SAC [2]
1.6.	ENROLLED	ES6	Summary of Screening and Run-In Status and Reasons for Screen and Run-In Failures	Journal Requirements	SAC [2]
1.7.	ENROLLED	NS1/SHELL	Summary of Number of Subjects by Region, Country and Centre	EudraCT/Clinical Operations Add in column for region, add a total for each region and a total for each country.	SAC [2]
Protocol Deviation					
1.8.	ITT	DV1	Summary of Important Protocol Deviations	ICH E3	SAC [2]
Population Analysed					
1.9.	ENROLLED	SP1	Summary of Study Populations	IDSL	SAC [1]
1.10.	Randomised	SP2A	Summary of Exclusions from the Intent-to-Treat and Safety Populations	IDSL	SAC [2]

CONFIDENTIAL

205687

Study Population Tables					
No.	Population	IDSL / Example Shell	Title	Programming Notes	Deliverable [Priority]
Demographic and Baseline Characteristics					
1.11.	ITT	DM1	Summary of Demographic Characteristics	ICH E3, FDAAA, EudraCT	SAC [1]
1.12.	ENROLLED	DM11	Summary of Age Ranges	EudraCT	SAC [2]
1.13.	ITT	DM5	Summary of Race and Racial Combinations	ICH E3, FDA, FDAAA, EudraCT	SAC [2]
1.14.	ITT	Shell	Summary of Nasal Polyps Disease History and Characteristics	Include Disease Duration (years/months); Number of previous surgeries; Number of Courses of OCS for NP in previous 12 months. Baseline Nasal Polyps endoscopy score (centrally read and investigator read); Baseline SNOT-22.	SAC [1]
1.15.	ITT	Shell	Summary of Previous Exacerbation History	To include separate summary of information for Asthma and COPD Exacerbation History	SAC [2]
Medical Conditions					
1.16.	ITT	MH4	Summary of Past Medical Conditions	ICH E3	SAC [2]
1.17.	ITT	MH4	Summary of Current Medical Conditions	ICH E3	SAC [2]
Prior and Concomitant Medications					

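### The time formulas in SAP 14.6.3 can give negative off-treatment time and overstated on-treatment time in Table 1.2, and the off-treatment line is also mis-bracketed

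*SAP*

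**What the plan says.** SAP 6.1 plans additional summary information "showing the amount of time within the 52-week treatment period considered as on-treatment, off-treatment and missing will be presented". The display is Table 1.2 in SAP 14.12.4, "Summary of Time On- and Off-Treatment by Withdrawal Scenario".

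SAP 14.6.3 supplies the formulas. It starts from a coverage convention, with "each dose viewed as providing therapeutic coverage for 4 weeks (28 days"). From this it derives:

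- years on-treatment: IP stop minus IP start plus 29, all divided by 365.25;
- years off-treatment, introduced by "The number of years off-treatment will be calculated as follows" and printed as "Date\ of\ Phase\ Conclusion - (IP\ stop\ date + 28)/365.25";
- years missing, for study withdrawals only: one minus the two quantities above.

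Neither of the first two formulas has an upper or lower limit.

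SAP 14.4.1.1, which assigns efficacy assessments to phases, does have one. For participants who did not stop product early, on-treatment ends at the "Earlier of Interventional Product Stop Date +28 days / Week 52 Visit Date". For those who stopped early, it ends at the earlier of stop plus 28 days and Date of Phase Conclusion. Neither document defines Date of Phase Conclusion.

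**The concern.** There are two separate faults in the off-treatment line.

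1. **Bracket.** As printed, a number of years is subtracted from a calendar date. The superseded plan reproduced in the same file has the same misplaced bracket with 29 in place of 28. The constant was edited and the bracket stayed, so a PDF conversion fault is unlikely. The on-treatment line just above brackets its date difference correctly.
2. **No cap or floor.** The 28-day credit is given even when the observed period ends sooner. The plan allows that: Visit 14 (last dose, Day 337) and Visit 15 (Day 365) are nominally exactly 28 days apart, and each has a window of ±7 days. Protocol 8.1 also lets a participant withdraw at any time.

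At stake is whether Table 1.2 shows possible durations. It tells the reader how much of the year each withdrawal scenario spent on product, off product or unobserved, which helps in judging the treatment-policy handling of discontinuation. The SAP's default summaries of continuous data (14.5.2) include the mean and the minimum, so a negative duration would be visible in the report.

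**Working it through.** **Inputs.** First dose on Day 1, Visit 14 on Day 337, Visit 15 on Day 365 and ±7-day windows (schedule of activities); last dose at Visit 14 (SAP 2.2); formulas from SAP 14.6.3. Results are in days before division by 365.25.

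**Nominal completer, bracket read as intended.** On = 337 − 1 + 29 = 365. Off = 365 − (337 + 28) = 0. This reproduces Day 365, so the formulas are right when visits fall exactly on schedule.

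**Literal reading.** Take SAS day numbers and an illustrative first dose on 1 June 2018 (day 21,336). The last dose is then 21,672 and phase conclusion 21,700. As printed: 21,700 − (21,672 + 28)/365.25 = 21,700 − 59.4 ≈ 21,641, against an intended 0. Years missing for a study withdrawer would become a large negative number.

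**Windows.** The gap from Visit 14 to Visit 15 can run from 28 − 14 = 14 days to 28 + 14 = 42 days. At the short end (Days 344 and 358), on = 344 − 1 + 29 = 372 days in a period of 358 days, and off = 358 − 372 = −14.

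**How many takers of the Week 48 dose.** If the timing of the gap is symmetric, the negative share is (1 − share with exactly 28 days)/2, so it cannot exceed one half. The documents give no distribution, so these are assumptions:

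| Assumed timing of Visits 14 and 15 | Negative off-treatment time |
|---|---|
| Independent, uniform over 15 whole days: 105 of 225 pairs | 46.7% |
| Rounded normal, SD 3 / 2 / 1 / 0.5 days | 45% / 43% / 36% / 24% |
| SD 2, Visit 15 late by 1 / 2 / 3 days on average | 30% / 19% / 11% |
| SD 2, Visit 15 early by 1 / 2 / 3 days on average | 57% / 70% / 81% |

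Under the uniform case, mean off-treatment time is 0 as written and 560/225 = 2.5 days when floored at zero.

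Study completers who stopped product at least one dose early are not affected while visits stay in window. Their smallest value is 358 − (316 + 28) = +14 days, since Visit 13 is on Day 309 and at latest Day 316.

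**Withdrawers, if phase conclusion is the date of leaving.** Last dose on Day 169:

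| Days from dose to leaving | On as written | Off as written | Sum | On capped | Off floored |
|---|---|---|---|---|---|
| 0 | 197 | −28 | 169 | 169 | 0 |
| 14 | 197 | −14 | 183 | 183 | 0 |
| 28 | 197 | 0 | 197 | 197 | 0 |
| 35 | 197 | 7 | 204 | 197 | 7 |

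**Effect on missing time.** As written, on + off = (stop − start + 29) + (conclusion − stop − 28) = conclusion − start + 1. The capped pair has the same sum. Missing time is therefore unaffected by the lack of a cap; only the bracket error damages it.

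**The case against.** The strongest reply is that this is a typographical slip plus a stated convention. No programmer would report 21,641 years, and the neighbouring line shows what was meant. The 28-day credit is declared openly, and the safety and adverse event phases (SAP 14.4.1.2 and 14.4.1.3) also run to stop plus 28 days with no Week 52 cap. SAP 14.4.1.1 classifies assessment dates; it is not a duration formula. The table is descriptive and has second delivery priority.

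Much of that stands. The literal result is a specification error rather than a likely output, and the 28-day credit is not wrong for extent of exposure. But the convention does not justify a negative duration, and SAP 6.1 confines this table to time inside the 52-week period.

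A withdrawer who attends the Early Withdrawal Visit 28 days after the last dose, as Protocol 8.1.2 asks, gets zero if that visit sets the phase conclusion. This also stands, so the withdrawer figures are conditional on an undefined date.

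A reader might go further and infer that negative values in completers cancel real off-treatment time in those who stopped product, so that the table understates it. The documents do not show this. Table 1.2 is split by the scenarios in SAP 14.7.2.3, which separate those completing product and study from those withdrawn from product. Some mixing within one scenario is possible, for example among those who stop product and later leave the study. A pooled row would also mix them, but the table shells are not in the documents.

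**Conclusion.** Wrong as written, with a small effect. The bracket error and the missing cap and floor follow from the text alone, as do the disagreement with SAP 14.4.1.1 and the poor fit with SAP 6.1. The maximum shift from off- to on-treatment time is 14 days for an in-window participant who took the Week 48 dose. It is 28 days for a withdrawer, on the assumption that phase conclusion is the date of leaving.

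It is tempting to say flatly that about half of completers are affected. The documents do not support that. One half is the ceiling under symmetric timing; the share is lower if visits cluster on schedule and can lie well outside that range if Week 52 visits run systematically early or late. It also concerns only those who took the Week 48 dose, not all study completers.

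A reader might also suspect the efficacy results. Nothing supports this: no efficacy test, p-value or sample size uses these quantities, and once the bracket is corrected missing time is right with or without the cap.

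**What to change.** In SAP 14.6.3, replace the two lines with:

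- years on-treatment = (min(IP stop + 28, Date of Phase Conclusion) − IP start + 1)/365.25;
- years off-treatment = max(0, Date of Phase Conclusion − (IP stop + 28))/365.25.

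Define Date of Phase Conclusion as the Week 52 visit for those completing to Week 52 and the study withdrawal date otherwise. The nominal completer stays at 365 and 0 days, the Day 344/358 example becomes 358 and 0, and the missing-time formula can stay as it is.

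The cost is two formula lines and one definition. There is one small downside: on-treatment years are now identical to Subject Years Exposure, and after capping they will differ from Table 1.21. A footnote should say that Table 1.21 keeps the uncapped 28-day therapeutic-coverage convention.

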## 6.2. Exclusion Criteria

Participants are excluded from the study if any of the following criteria apply:

CONCURRENT CONDITIONS/MEDICAL HISTORY

 
1. As a result of medical interview, physical examination, or screening investigation the physician responsible considers the participant unfit for the study.
 
2. Cystic fibrosis
 
3. Eosinophilic granulomatosis with polyangiitis (also known as Churg Strauss syndrome), Young's, Kartagener's or dyskinetic ciliary syndromes
 
4. Antrochoanal polyps
 
5. Nasal septal deviation occluding one nostril
 
6. Acute sinusitis or upper respiratory tract infection (URTI) at screening or in 2 weeks prior to screening
 
7. Ongoing rhinitis medicamentosa (rebound or chemical induced rhinitis)
 
8. Participants who have had an asthma exacerbation requiring admission to hospital within 4 weeks of Screening.
 
9. Participants who have undergone any intranasal and/or sinus surgery (for example polypectomy, balloon dilatation or nasal stent insertion) within 6 months prior V1
 
10. Participants where NP surgery is contraindicated in the opinion of the Investigator
 
11. Participants with a known medical history of HIV infection.
 
12. Participants with a known, pre-existing parasitic infestation within 6 months prior to Visit 1.
 
13. Participants who are currently receiving, or have received within 3 months (or 5 half lives – whatever is the longest) prior to screening visit, radiotherapy or investigational medications/therapies.
 
14. Participants with a history of sensitivity to any of the study medications, or components thereof or a history of drug or other allergy that, in the opinion of the investigator or GSK Medical Monitor, contraindicates their participation. Aspirin-sensitive participants are acceptable.
 
15. Participants with a history of allergic reaction to anti-IL-5 or other monoclonal antibody therapy.
 
16. Not willing to be removed from a waiting list for NP surgery (if on one) or have pre-planned surgery date cancelled if randomized A waiting list is a list of patients waiting for a non-emergency or elective surgical procedure.
 
17. Participants that have taken part in previous mepolizumab, reslizumab, dupilumab or benralizumab studies
 

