### **9.1.3. Critical procedures performed at Screening (Visit 1)**

- Medical history including smoking status, history of sinusitis, NP history (including NP surgery), aspirin sensitivity, history of asthma, courses of rescue corticosteroids in the past 12 months, asthma exacerbation history in the previous 12 months, smoking history.
- Therapy/Concomitant medication history, including use of mepolizumab, omalizumab or previous biologics in the past 12 months.

- Cardiovascular medical history/risk factors (as detailed in the eCRF). This assessment must include a review of the participant responses to the cardiovascular assessment questions and height, weight, blood pressure, smoking history, medical conditions, and family history of premature cardiovascular disease.
- Physical exam
- Vital signs
- Dispensing and training of eDiary
- Nasal obstruction VAS symptom score
- Overall VAS symptom score
- Resting 12-lead ECG
- Laboratory tests. These should include:
  - Chemistry
  - Haematology with differential count
  - Hepatitis B Surface Antigen and hepatitis C antibody
  - Urinalysis
  - Urine pregnancy test- for all WOCBP
  - FSH will be assessed to confirm child-bearing status (if applicable)
  - Parasitic screening (only in countries with a high-risk or in participants who have visited a high-risk country)
- Endoscopic NP score
- Review of Inclusion/Exclusion criteria
- Review of exacerbations, SAEs

Procedures conducted as part of the participant's routine clinical management [e.g. blood eosinophil counts] and obtained prior to signing of informed consent may be utilised for screening or baseline purposes provided the procedure meets the protocol-defined criteria and has been performed within the timeframe defined in the SoA.

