5.4.2. Examination of Subgroups

This section details the subgroups of interest within this study. For each co-primary endpoint, a separate exploratory analysis within each of the subgroup categories will be carried out. Subgroup analyses for all other endpoints are detailed in the statistical methods/analysis sections. Unless otherwise stated no formal hypothesis testing in subgroups of the population will be performed.

Subgroup	Categories
Participants with Asthma	Concurrent asthma, No concurrent asthma
Aspirin Exacerbated Respiratory Disease (AERDS)	Current AERDS, No Current AERDS
Number of previous surgeries	1, 2, >2
Baseline Blood Eosinophil Categories (GI/L)	≤0.3 GI/L; >0.3 to ≤0.5 GI/L; >0.5 to ≤0.7 GI/L; >0.7 GI/L
Region	Europe, United States, Rest of World
Age	18-<40, 40-<65, ≥65 years
Gender	Male, Female
Race	African American/African Heritage, White, Asian, Other

If, following unblinding, the analysis model within a subgroup category fails to converge due to small numbers of participants, the model will be rerun with consideration of further refining regions or if required exclusion of the region covariate. Failing this, subgroup categories may be further refined when possible, otherwise only a descriptive summary of the data will be presented. Footnotes will clearly identify the covariates included in the analysis model.

There is a biological rationale for potentially observing greater efficacy with increasing levels of baseline blood eosinophils. Except for baseline blood eosinophils, differential treatment effects are not expected for any of the other subgroups listed above and therefore any differences in efficacy of mepolizumab compared to placebo observed in subgroup categories will be viewed as exploratory.

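### SAP 14.6.3 defines 'Current AERDS' by any current drug allergy, so exploratory Tables 2.7 and 2.20 can apply the AERD label to participants who do not have it

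*SAP*

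**What the plan says.** SAP 14.6.3, under its AERDS heading, gives one criterion for membership: "Current AERDS: Subjects with a response of 'Current' for the medical condition of 'Drug Allergy". Every other answer to that item, and a missing answer, puts the participant in the complementary category. No drug is named. The 'Asthma' item, defined just above for a different subgroup, plays no part.

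SAP 5.4.2 lists the subgroup under the full disease name with the categories "Current AERDS, No Current AERDS". It plans no formal testing within subgroups unless stated elsewhere, and says that any difference in efficacy "observed in subgroup categories will be viewed as exploratory". SAP 14.12.6 assigns two displays to it: Table 2.7 for the nasal polyps score and Table 2.20 for the nasal obstruction VAS. Both have delivery priority SAC [2].

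On who can be in the trial, exclusion 14 in Protocol 6.2 removes sensitivity to study medications and otherwise only "a history of drug or other allergy that, in the opinion of the investigator or GSK Medical Monitor, contraindicates their participation". It then adds: "Aspirin-sensitive participants are acceptable". Exclusion 15 removes "Participants with a history of allergic reaction to anti-IL-5 or other monoclonal antibody therapy". The Visit 1 medical history in Protocol 9.1.3 includes "history of sinusitis, NP history (including NP surgery), aspirin sensitivity, history of asthma".

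**The concern.** The label is narrower than the rule behind it. AERD is respiratory disease linked to aspirin, whereas a current drug allergy could be to any drug and need involve no airway disease. If participants with unrelated drug allergies are in the group, Tables 2.7 and 2.20 describe a mixture under a specific disease name. A reader who takes the AERD effect from those tables would be reading the effect in a different population.

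The stake is the interpretation of two exploratory tables. AERDS is not a covariate in any efficacy model listed in SAP 5.4.1 and does not enter the testing hierarchy in SAP 5.5.

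**Working it through.** No arithmetic applies. The documents give no count of participants with a drug allergy, aspirin sensitivity or AERD, so the check sets the passages side by side.

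1. **What the rule takes in.** Its only input is the 'Drug Allergy' response (SAP 14.6.3). A 'Current' answer is sufficient, and nothing in either document limits that answer to aspirin or NSAIDs. The reporting and analysis plan of 05-SEP-2019, included in the same SAP file, has the same rule, so this is not a fault of text extraction.

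2. **Whether other drug allergies can be present.** Exclusion 14 removes sensitivity to study medications and those allergies that the investigator or medical monitor considers a bar to participation. Exclusion 15 removes reactions to monoclonal antibodies. An allergy to some other drug, not judged a bar, passes both.

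3. **Whether the protocol treats the two ideas as one.** It does not. Exclusion 14 speaks of drug allergy in general and then makes a separate statement about aspirin-sensitive participants. Protocol 9.1.3 names aspirin sensitivity as a Visit 1 history item. The SAP rule uses the broad idea and not the specific one.

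4. **Whether respiratory disease is required.** It is not. The neighbouring subgroup in 14.6.3 defines concurrent asthma from a 'Current' response for 'Asthma', a field that matches its label. The AERDS rule does not draw on that field.

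5. **Tracing one case.** Take a participant with a current allergy to a drug other than aspirin or an NSAID, not judged a bar to participation, and with no asthma. Steps 1 to 4 allow randomisation and then assign this participant to 'Current AERDS' in Tables 2.7 and 2.20.

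6. **Whether another display settles the matter.** Table 1.17, "Summary of Current Medical Conditions", covers the same kind of data. Its layout is not in the documents, and SAP 14.13 says shells are available on request. It may or may not separate aspirin from other drugs.

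**The case against.** The strongest reply is that the eCRF is not in the documents and may resolve the matter. Protocol 9.1.3 names aspirin sensitivity and no general drug-allergy item among the Visit 1 history items, and SAP 14.6.3 puts the 'Drug Allergy' field under the AERDS heading. The field may therefore be where aspirin sensitivity is recorded, possibly nothing else. If so, no unrelated allergy reaches the group and only an explanatory sentence is missing. This stands as a limit on the point: the documents show a rule that permits mislabelling, not that anyone is mislabelled.

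A second reply is that little depends on it. The classifier comes from history taken at screening, so any misclassification is unrelated to treatment arm and the comparison within the labelled group remains randomised. SAP 5.4.2 plans no formal subgroup testing and expects no differential effect for this subgroup. This also stands, and it is why the item is minor.

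A reader might go further and infer that the AERD subgroup is contaminated to a material degree, or that its treatment comparison is biased. The documents support neither. They give no prevalence from which to size a mixture, and a group with too narrow a name still yields a valid randomised comparison for the group actually formed.

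The objections do not remove the mismatch in the text. As the SAP stands, neither a programmer nor a reader can tell from it whether the label is right.

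**Conclusion.** The point holds as a minor defect of definition. Followed as written, SAP 14.6.3 can place participants without AERD in the group that Tables 2.7 and 2.20 call AERD. The size cannot be determined from the documents, and it is nil if the eCRF field is specific to aspirin or NSAIDs. I attach no percentage, because any figure would rest on prevalences that the documents do not give.

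The conclusion rests on reading the rule literally and on the eligibility criteria as printed. The co-primary tests, the hierarchy, the type I error rate and the sample size are unaffected.

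**What to change.** Check the eCRF and make one of these changes before unblinding:

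- **If aspirin or NSAID can be identified:** in SAP 14.6.3, derive 'Current AERDS' from aspirin/NSAID sensitivity (the Visit 1 history item, or a drug allergy identified as aspirin/NSAID) combined with a 'Current' response for 'Asthma'. Restricting the drug alone is not enough, since it would not establish respiratory disease.
- **If it cannot be identified:** rename the subgroup 'Current drug allergy' in SAP 5.4.2, 14.6.3 and the titles of Tables 2.7 and 2.20.
- **If the field is already specific to aspirin/NSAID:** state that in 14.6.3.

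The cost is one sentence and one derivation, or one relabelled subgroup with two table titles. Where the narrower definition removes participants, the labelled group is smaller and its confidence interval somewhat wider. Fixing the definition before unblinding also avoids choosing it with the results in view.
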